6.3 STATISTICAL ANALYSES

Pre-operative patients: Toxicity data will be graded and tabulated. A one-sample one-sided chi-square test will be performed to test the null hypothesis that the wound complication rate is 45% (same as photon). Patients must have a minimum of 4 months of follow-up after surgery to be evaluable for this analysis.

CONFIDENTIAL

This material is the property of the University of Pennsylvania. Do not disclose or use except as authorized in writing by the study sponsor

Post-operative patients: Toxicity data will be graded and tabulated. In the study by Davis et al (Radiother and Oncol 75, 2005), the grade 2+ fibrosis rate was 48%, joint stiffness 23% and edema 23%. Since fibrosis is the most common post-operative toxicity, it is considered the primary endpoint and a one-sample one-sided chi-square test will be performed at the 5% significance level to test the null hypothesis of 50% (same as photon). Joint stiffness and edema are less frequent toxicities and will be treated as secondary endpoints. The null hypothesis is that the grade 2 or higher rate is 25% (same as photon) for these endpoints. Patients must have a minimum of 2 years of follow-up after surgery to be evaluable for this analysis.

Acute toxicity (Late toxicity): Toxicities will graded and tabulated by stratum.

Clinical Efficacy: For pre-operative patients, the RECIST response rate (CR + PR based on RECIST) and 90% exact CI will be computed. For each stratum, time to local recurrence, time to distant recurrence, PFS and OS will be estimated by Kaplan-Meier analysis.

Exploratory Analyses of [¹⁸F]-EF5:

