With 12 patients per year enrolled to each stratum and accounting for required follow-up time for feasibility and toxicities, this study should be active for 7 years. Twelve pre-operative and 12 post-operative patients will be enrolled on the feasibility portion of the trial. If feasibility and safety are acceptable then 40 evaluable pre-operative patients and 40 evaluable post-operative patients with STS of the lower extremity (each group includes evaluable patients from the feasibility stage) will be enrolled in the phase II portion of the trial. Up to 50 pre-operative patients may need to be enrolled to yield 40 evaluable patients with lower extremity STS who undergo surgery and have 4 months of follow-up post-surgery. With 40 evaluable patients, there will be 84% power for a chi-square test at one-sided 5% type I error to test a grade 2 or higher wound complication rate of 45% versus an alternative rate of 25%.

Similarly, up to 50 post-operative patients may need to be enrolled to yield 40 evaluable patients with lower extremity STS who receive post-operative radiotherapy and remain on-study for 2 years from the end of radiotherapy. With 40 evaluable patients, there will be 83% power for a chi-square test at one-sided 5% type I error to test a grade 2 or higher fibrosis rate of 50% versus an alternative rate of 30%. In addition, there will be 80% power for chi-square tests at one-sided 2.5% type I error to test grade 2 or higher joint stiffness and

CONFIDENTIAL

edema, each with rates of 25% versus alternative rates of 9%. These secondary analyses will be tested at a 2.5% significance level, to control the overall type I error.

All correlative analyses of hypoxia and clinical outcome are exploratory. Results from this unique study will be used to estimate the magnitude of the associations for both RECIST response and time-to-event outcomes and will provide important guidance for future studies of the prognostic importance of hypoxia in STS patients.

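### The 80% power stated for joint stiffness and edema is not attained: the planned one-sided 2.5% chi-square test with 40 patients has about 71% power for 25% versus 9%.

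*Combined protocol and SAP*

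**What the plan says.** Section 6.3 makes grade 2 or higher fibrosis the primary post-operative endpoint and treats joint stiffness and edema as secondary. For those two it fixes the reference rate: "The null hypothesis is that the grade 2 or higher rate is 25% (same as photon) for these endpoints". The fibrosis test in the same paragraph is described as a one-sample, one-sided chi-square test.

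Section 6.4 gives the power. For fibrosis (50% versus 30%) it says: "With 40 evaluable patients, there will be 83% power for a chi-square test at one-sided 5% type I error". It then adds that "there will be 80% power for chi-square tests at one-sided 2.5% type I error to test grade 2 or higher joint stiffness" and edema, "each with rates of 25% versus alternative rates of 9" per cent. On the level, it says: "These secondary analyses will be tested at a 2.5% significance level, to control the overall type I error". For wound complications in the pre-operative stratum (45% versus 25%, also 40 patients), it says "there will be 84% power for a chi-square test at one-sided 5% type I error".

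**The concern.** All the inputs needed to check the 80% are in the plan, and they do not produce it. The usual normal-approximation formula for a one-sample chi-square test comes within a point of the other two powers in section 6.4, but falls more than 8 points short for joint stiffness and edema.

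The two endpoints are more than descriptive. Section 1 names them, with fibrosis, as examples of the functional outcome in the post-operative Phase II primary objective, and section 6 gives them their own null rate and significance level. Anyone interpreting a non-significant result would use the stated power to judge how much weight it carries, and would overrate it.

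**Working it through.** **Inputs, all from sections 6.3 and 6.4.** n = 40 evaluable post-operative patients; null rate p0 = 0.25; alternative p1 = 0.09; one-sided level 0.025 (critical z = 1.960); one-sample chi-square test against a fixed rate.

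**Formula.** With the null variance under the null and the alternative variance under the alternative:

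power = Φ{ [p0 − p1 − z·√(p0(1−p0)/n)] / √(p1(1−p1)/n) }

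**Step 1: the plan's other two powers (one-sided 5%, z = 1.645, n = 40).**

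- Wound complication, 45% versus 25%: (0.20 − 1.645 × 0.0787)/0.0685 = 1.03, so power is 84.9%. The plan states 84%.
- Fibrosis, 50% versus 30%: (0.20 − 1.645 × 0.0791)/0.0725 = 0.97, so power is 83.3%. The plan states 83%.

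**Step 2: the same formula for joint stiffness and edema.**

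- Null standard error: √(0.25 × 0.75/40) = 0.0685.
- Alternative standard error: √(0.09 × 0.91/40) = 0.0452.
- (0.16 − 1.960 × 0.0685)/0.0452 = 0.57, so power is 71.6%. The plan states 80%.

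**Step 3: exact power of the test as it would be run.**

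- At 4/40, z = (0.25 − 0.10)/0.0685 = 2.19, which exceeds 1.960: reject.
- At 5/40, z = (0.25 − 0.125)/0.0685 = 1.83: do not reject.

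| Rule | Size, P(X ≤ c) at 25% | Power, P(X ≤ c) at 9% |
|---|---|---|
| Reject at ≤ 4 of 40 (the planned test) | 1.60% | 71.0% |
| Reject at ≤ 5 of 40 | 4.33% | 85.3% |

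The second rule passes 80% but breaks the 2.5% level.

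**Step 4: could any valid test reach 80%?** The most powerful test of exact size 2.5% rejects at 4 or fewer and randomises at 5 events with probability (0.0250 − 0.0160)/0.0272 = 0.329. Its power at 9% is 0.7103 + 0.329 × 0.1432 = 0.757. So 75.7% is the ceiling for 40 patients.

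**Step 5: what alternative would give 80%?** With the rule of 4 or fewer, exact power reaches 80% at a true rate of 7.8%; the normal approximation reaches it at 8.0%. At a rate of 8%, power is 79.8% by the normal approximation and 78.7% exact.

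**The case against.** The strongest reply is that the 80% may come from a different approximation used throughout, not from a slip in one figure. The arcsine (variance-stabilised) formula gives 84.9%, 83.1% and 79.1% for the three designs, against the stated 84%, 83% and 80%, so it fits all three to within about a point. The plan names no power formula, so its origin cannot be settled, and it would be unfair to insist that one figure was computed differently from the others. That part of the reply stands.

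It does not rescue the number. Power belongs to the test that will be run, and the plan specifies a chi-square test at one-sided 2.5%. The arcsine formula is inaccurate for a rate as low as 9% with 40 patients, and the result it gives lies above the 75.7% ceiling for any valid test.

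A second reply is that exact power is a stricter standard than the plan applied to its primary endpoints. It is true that the exact powers there are also below the stated ones: 82.1% for wound complication (reject at ≤ 12 of 40) and 80.7% for fibrosis (reject at ≤ 14 of 40), against 84% and 83%. Those gaps are about 2 points and both powers stay above 80%. The gap here is about 9 points, and the normal approximation shows nearly all of it.

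A third reply is that nothing in the design depends on this figure. That is correct and limits the weight of the point.

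**Conclusion.** The stated 80% is wrong for the test as specified. Power for 25% versus 9% is 71.0% exact, or 71.6% by the normal approximation, an overstatement of 8 to 9 points for each of the two secondary endpoints. The chance of missing the plan's own target effect is about 29% instead of 20%.

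This rests only on figures in sections 6.3 and 6.4, and on reading the secondary tests as one-sample chi-square tests of the same form as the fibrosis test. The consequence is confined to joint stiffness and edema. The 40 evaluable patients are justified by the primary endpoints, whose stated powers hold closely enough.

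**What to change.** In section 6.4, make one of two changes:

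- Keep 25% versus 9%, and state power of about 71%, adding that the test rejects at 4 or fewer events in 40 and has an attained size of 1.6%.
- Keep a power of roughly 80%, and change the alternative to about 8%, giving both the normal-approximation value (79.8%) and the exact one (78.7%).

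The first is preferable because it leaves the target effect unchanged. In either case, name the method used for the power figures.

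The cost is a revised figure and a sentence. Sample size, tests and significance levels do not change; the plan only has to accept a less favourable statement of its secondary power.

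### Testing joint stiffness and edema at 2.5% each, ungated beside a 5% fibrosis test, holds the error at 5% within the secondary pair but not overall

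*Combined protocol and SAP*

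**What the plan says.** Section 6.3 (post-operative patients) chooses one primary endpoint: "Since fibrosis is the most common post-operative toxicity, it is considered the primary endpoint". It specifies that a "one-sample one-sided chi-square test will be performed at the 5% significance level to test the null hypothesis of 50" percent, the rate assumed for photons.

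The other two functional endpoints rank lower: "Joint stiffness and edema are less frequent toxicities and will be treated as secondary endpoints". Their null is also fixed: "The null hypothesis is that the grade 2 or higher rate is 25% (same as photon) for these endpoints".

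Section 6.4 repeats the one-sided 5% for fibrosis (83% power, 50% against 30%, 40 evaluable patients). For stiffness and edema it says "there will be 80% power for chi-square tests at one-sided 2.5% type I error", for 25% against 9%. It closes with "These secondary analyses will be tested at a 2.5% significance level, to control the overall type I error".

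Neither section makes the secondary tests conditional on fibrosis, sets a testing order or passes alpha from one test to another. The documents do not say which tests *overall* covers and give no numerical limit for it.

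**The concern.** A Bonferroni split of 5% over two tests gives 2.5% each and protects those two tests as a pair. It leaves no allowance for a third test that has already used 5%. As written, all three tests are run and any of them can produce a formal finding, so the error over the set exceeds 5%.

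What is at stake is the status of a stiffness or edema result when fibrosis misses. Section 1 puts fibrosis, stiffness and edema together as examples of the functional outcome in a single post-operative Phase II primary objective. A significant secondary result could therefore be offered in support of that objective, with the sentence in section 6.4 cited as evidence of error control that the procedure does not supply across the three tests.

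**Working it through.** **Inputs.** Sections 6.3 and 6.4 give N = 40 evaluable; fibrosis null 50%, alternative 30%, one-sided 5%; stiffness and edema null 25%, alternative 9%, one-sided 2.5% each. The correlation among the endpoints is not given and is varied below as an assumption.

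**1. The plan's own power figures.** The arcsine formula is Φ(2·|asin√p0 − asin√p1|·√n − z(1−α)).

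- Fibrosis: 2 × |0.7854 − 0.5796| × √40 − 1.645 = 0.958, so power is 83.1% (stated 83%).
- Each secondary: 2 × |0.5236 − 0.3047| × √40 − 1.960 = 0.809, so power is 79.1% (stated 80%).

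Both are reproduced to within a point. Exact binomial power is 80.7% for fibrosis and 71.0% for each secondary, so the stated 80% depends on the approximation.

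**2. Nominal error with all three nulls true.**

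- Upper bound: 5% + 2.5% + 2.5% = 10%.
- Independent tests: 1 − 0.95 × 0.975² = 9.69%.
- Secondary pair alone: at most 5%; 1 − 0.975² = 4.94% if independent.
- Equally correlated normal statistics, three tests: 9.0% at 0.3, 8.3% at 0.5, 7.3% at 0.7, 5.4% at 0.95. The error comes down to 5% only at essentially perfect correlation.

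**3. Attained error at n = 40.** The uncorrected one-sided test rejects as follows.

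- Fibrosis: 14 or fewer events (z = −1.90; 15 events give −1.58, short of −1.645). Exact size 4.03%.
- Each secondary: 4 or fewer events (z = −2.19; 5 events give −1.83, short of −1.960). Exact size 1.60%.

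If independent, the three-test error is 1 − (1 − 0.0403)(1 − 0.0160)² = 7.1%, and the pair alone gives 1 − (1 − 0.0160)² = 3.2%. Simulation with a shared latent normal variable (100,000 trials per row) gives:

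| Assumed latent correlation | Any of three | Secondary pair |
|---|---|---|
| 0 | 7.2% | 3.3% |
| 0.3 | 6.8% | 3.1% |
| 0.5 | 6.7% | 3.1% |
| 0.7 | 6.5% | 3.1% |
| 0.9 | 5.8% | 2.6% |

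A false secondary finding after a non-significant fibrosis test occurs in about 3% of trials if independent (0.9597 × 0.0318) and about 2.5% at correlation 0.7 (simulated 6.54% less 4.07% for fibrosis).

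These attained figures are specific to 40 evaluable patients. Because the counts are discrete, the independence figure for 36 to 50 evaluable patients runs from 6.3% (n = 47) to 11.1% (n = 43). The top of that range arises because the uncorrected tests can exceed their own nominal levels at some sample sizes.

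**4. Effect of a gate.** Suppose the secondaries are tested only after a significant fibrosis result. If the fibrosis null is true, any false finding requires a false fibrosis rejection, so the nominal error is at most 5%. If it is false, only the two secondaries can err, again at most 2 × 2.5% = 5%. Power for a given secondary through the gate, if independent, is 0.831 × 0.791 = 66% (arcsine) or 0.807 × 0.710 = 57% (exact), and higher with positive correlation.

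**The case against.** The strongest reply is that the sentence is about the secondary analyses, and that two tests at 2.5% sum to exactly 5%. Read as a Bonferroni split within the pair, beside a separately designated primary, it is true. Strict familywise control over primary and secondary endpoints is also a convention of confirmatory trials, and this is a single-arm phase II stratum of 40 compared with fixed historical rates. A gate would be a preference, and it takes power from tests for which the plan states 80%.

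Much of this stands. The narrower reading is arithmetically possible, and adopting it explicitly would settle the matter. The gate's cost is real. What does not stand is leaving the sentence alone. It says *overall* without qualification, section 1 places all three endpoints under one objective, and section 6.4 labels the hypoxia analyses exploratory while giving stiffness and edema formal levels.

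A reader might also infer more than the documents support:

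- That the fibrosis test is inflated. It has its own 5% level (4.03% attained at n = 40), and the secondaries do not alter it.
- That a stiffness or edema test lacks its stated error rate. Each has a nominal 2.5% (1.60% attained at n = 40) whatever fibrosis shows; only the union of the three tests exceeds 5%.
- That the trial in practice runs at 10%. That is the nominal upper bound; at n = 40 the attained excess over 5% is about 1 to 2 points.
- That the plan intends to present a secondary result as proof of benefit after fibrosis fails. Nothing in it says so.
- That the pre-operative wound test belongs in the sum. It is a separate 5% test in different patients.

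**Conclusion.** The point holds in a limited form. The ungated 2.5% level controls the error at 5% within stiffness and edema, but not across the three post-operative tests. There it is up to 10% nominally (9.7% if independent) and about 6% to 7% attained at 40 evaluable patients. The attained range rests on the uncorrected one-sided test, the stated null rates and an assumed latent correlation between 0 and 0.9. The finding concerns only what may be claimed for the two secondary endpoints. It is worth correcting before analysis because the plan itself asserts the property and the correction is short.

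**What to change.** Amend sections 6.3 and 6.4 in one of two ways.

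(a) **Gate the secondaries.** State that joint stiffness and edema are tested formally, each at one-sided 2.5%, only if fibrosis is significant at one-sided 5%, and are otherwise reported descriptively with confidence intervals. Add that the 80% secondary power is before the gate, and give the gated figure: about 66% by the arcsine method or 57% exact if independent, higher with positive correlation. N, the fibrosis test and its power do not change. The cost is that lower secondary power, with no formal secondary finding when fibrosis is not significant.

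(b) **Narrow the statement.** Keep the ungated tests and replace the purpose clause at the end of the sentence. The new wording should say that 2.5% each controls the error at 5% within the two secondary endpoints only, not jointly with fibrosis, and that a secondary result after a non-significant fibrosis test is supportive only. This changes no test, sample size or power. The cost is giving up the broader assurance.

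Reaching 5% across all three tests without a gate, for example with 2.5% for fibrosis and 1.25% for each secondary, would cut arcsine power to about 74% and 70%, so it is harder to justify here.

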7 SAFETY AND ADVERSE EVENTS

The investigator or research staff will be responsible for detecting, documenting and reporting all events that meet the definition of an AE or SAE as defined in this protocol.

Definition

An **adverse event** (AE) is any unfavorable and unintended sign, symptom, sign (including abnormal laboratory findings), illness/disease (new or exacerbated) or experience that develops or worsens in severity temporally associated with the use of the investigational agent/device/procedure. Intercurrent illnesses or injuries should be regarded as adverse events. Abnormal results of diagnostic procedures are considered to be adverse events if the abnormality:

- results in study withdrawal
- is associated with a Serious Adverse Event (SAE)
- is associated with clinical signs or symptoms
- leads to additional treatment or to further diagnostic tests
- is considered by the investigator to be of clinical significance

Radiation Effect

Radiation side effects are typically divided into those that occur acutely (during radiation and up to 3 months after radiation) and those that occur later (>3 months post-radiation). Common acute radiation side effects include fatigue, skin irritation or erythema. Typically, these side effects can be controlled with medication. Late side effects that are unlikely to occur are paralysis or cardiac complications. Another rare but serious late side effect is the development of second tumors. It is hoped that proton radiation will substantially reduce both acute and late side effects by reducing the amount of normal tissue that is irradiated.

For acute radiation effect, through post treatment day 90 of treatment, CTCAE 4.0 will be employed. Late radiation effects will be evaluated using the RTOG/EORTC Late Radiation Morbidity Scoring System.

Assessing and Recording Adverse Events

All Adverse and Serious Adverse Events will be assessed using NCI Common Terminology Criteria for Adverse Events version 4.0 (CTCAE 4.0) with the exception of late radiation effects as noted above.

Reporting of Serious Adverse Events

(a) IRB Notification by Investigator

All events meeting the Penn IRB SOP for Unanticipated Events posing risks to subjects or others will be reported to the IRB as follows:

Unanticipated problems are:

- (1) Unforeseen; and
- (2) indicate that participants are at increased risk of harm.

CONFIDENTIAL

The IRB requires investigators to submit reports of the following problems within 10 working days **with one exception**. The one exception for prompt reporting within 10 days applies to death of a research participant as noted below.

Adverse Event (regardless of whether the event is serious or non-serious, onsite or off-site) that occurs any time during or after the research study, which in the opinion of the principal investigator is both unexpected and related to research procedures.

Note: An event is "unexpected" when its specificity and severity are not accurately reflected in the protocol-related documents, such as the IRB-approved research protocol, any applicable investigator brochure, and the current IRB-approved informed consent document, and (b) other relevant sources of information, such as product labeling and package inserts); An event is "related to the research procedures" if the event is deemed probably or definitely related.

If the adverse event involved death as unforeseen and indicates participants or others are at increased risk of harm, report in **three days**.

(b) Data and Safety Monitoring Committee (DSMC) Notification by Investigator

All Serious Adverse Events (SAEs), regardless of grade, expectedness or attribution must be reported to the DSMC within **30 days**. Deaths that are possibly, probably or definitely related to the protocol treatment/experience must be reported within **24 hours**. SAEs should be reported to the DSMC for **six months from the date the last subject was treated**.

(c) FDA Notification by Sponsor

The study investigator shall notify the FDA by telephone or by facsimile transmission of any unexpected fatal or life-threatening experience associated with the use of the protocol agent/treatment/device as soon as possible but no later than 7 calendar days of knowledge of the event. If all details of the event are not immediately known, a partial report should be sent to ensure compliance with reporting timeframes. A follow-up report shall be submitted as soon as the relevant information is available.

If a previous event that was not initially deemed reportable is later found to fit the criteria for reporting, the study sponsor will submit the event in a written report to the FDA as soon as possible, but no later than 15 calendar days from the day the determination is made.

(d) Varian Biosynergy, Inc.

All Unanticipated problems including Serious Adverse Events related to the study drug should be reported promptly to the Sponsor within 24 hours of discovery of the event. All other adverse events will be reported to Varian in an Annual Report at the Company's Request.

Stopping Rules

(Please see Section 6 for "Stopping Rules")

8 MEDICAL MONITOR

Data Safety and Monitoring Committee

The University of Pennsylvania Cancer Center (UPCC) through the Data and Safety Monitoring Committee (DSMC) will be reviewing this clinical trial. It is anticipated that with approval, the committee's

CONFIDENTIAL

role will be to ensure that the rights and well-being of all subjects are protected and that patients are treated in full compliance with the study treatment and parameters specified in the protocol. The Data and Safety Monitoring Committee (DSMC) is responsible for overseeing the process of monitoring of studies and the conduct of audits. The investigators on this study are responsible for the continuous, close monitoring of subjects enrolled on this trial.

A DSMC audit of this trial will be performed every six months for as long as the trial remains open for accrual. The principal investigator will be notified in advance of the selection of their protocol for review. Three randomly selected patients or 10% of the total accrual, whichever is higher will be audited. A written report is provided to the principal investigator following this audit. Any rating less than satisfactory would warrant a repeat full review at the time of the next scheduled audit or sooner, depending upon the extent of the deficiencies found. Substantial protocol deviations will be reported to the Director of the Cancer Center and the Associate Director for Clinical Research for consideration of appropriate administrative action, such as suspending accrual to the protocol.

A Medical Monitor, [name]., who is not directly involved in this trial and is not collaborating with the investigator in any other trials, has been selected for this trial. The Medical Monitor will review adverse events, safety data, and activity data observed in the ongoing clinical trial. The Medical Monitor may recommend reporting of adverse events and relevant safety data not previously reported, and may recommend suspension or termination of the trial. The summary reports of all discussions of adverse events will be submitted to the Data and Safety Monitoring Committee (DSMC) on a bi-yearly basis or more frequently if appropriate.

The Principal Investigator or his/her designee of the trial will present to the Medical Monitor all adverse events observed in-patients, any activity data obtained, and whether those data invoked any stopping criteria in the clinical protocol. Adverse event reporting will follow the NCI guidelines. Results of the data from toxicology or other animal studies that are relevant will be discussed. Other information related to the safety and efficacy of the clinical study will be discussed. This includes information of similar investigational materials used in different studies.

Medical Monitoring

It is the responsibility of the Principal Investigator to oversee the safety of the study at his/her site. This safety monitoring will include careful assessment and appropriate reporting of adverse events as noted above, as well as the construction and implementation of a site data and safety-monitoring plan (see Section 11.2). Medical monitoring will include a regular assessment of the number and type of serious adverse events.

The Medical Monitor will be [name]. (a physician who is not directly involved in the trial and is not collaborating with the sponsor/investigator in any other trial). Because of [name] background and experience in medical oncology, he is an appropriate Medical Monitor (MM) for this study. In the role, he will review all AEs including grading, toxicity assignments, dose modifications, appropriateness of dose escalation and all other safety data and activity data observed in the ongoing clinical trial along with discussing relevant animal and toxicology studies and similar investigational agents. The MM may recommend reporting of adverse events and relevant safety data not previously reported and may recommend suspension or termination of the trial. The investigator will meet with the MM every three months. Serious and unexpected issues will be handled on an ad hoc basis through calls or e-mail. Documentation of MM activity will be maintained in the study specific Regulatory Binder. Copies of an MM report requiring action on the part of the PI to protect subject safety or study integrity must be submitted to the DSMC within 10 business days.

Protocol Deviations/Exceptions

CONFIDENTIAL

This material is the property of the University of Pennsylvania. Do not disclose or use except as authorized in writing by the study sponsor

Occasionally, the investigator may need to deviate from the approved protocol. Deviations are categorized as reportable and non-reportable. Reportable deviations may be urgent or not. Urgent deviations may occur on the spot as necessary to protect the safety of a study subject and do not allow enough time for reporting in advance. However, they must be reported as soon as possible.

All deviations from the study protocol will be handled as follows:

Eligibility - Deviations from established eligibility criteria will not be allowed. If the investigator believes that a subject would truly benefit from the protocol therapy and there are no other viable options, then the protocol should be amended to reflect the change in restrictions. There may be situations where the deviation from eligibility may not warrant a study amendment (e.g. a necessary test/procedure being a few days outside of the eligibility window, subject taking a concomitant medication within recent timeframe etc.). These deviations must still be reviewed and approved in advance of enrolling the subject.

The IRB must be notified of the planned deviation and a copy of all applicable amended study documents must be sent to the IRB. The planned deviation must also be submitted to the DSMC for evaluation. The DSMC does not approve deviations but rather provides an unbiased assessment of the appropriateness of the request. Both committees must be given sufficient time to review the request, gather additional information as necessary and make a decision.

Other Reportable - Deviations that affect the protocol treatment administration (i.e. dose administered, route/method of administration etc.), dose adjustment schema, stopping rules, modification to follow-up, removal of safety assessments/follow-up visits, accrual goal or any deviation that may affect the study outcome analysis or study integrity must be approved by the IRB and reviewed by the DSMC.

Non-Reportable - During the course of a study, there may be times when deviations are outside of the control of the investigator (i.e. subject not showing up for a study visit, lab errors, subject confusion etc.). These type of deviations are not reportable (unless they occur at a level that impacts any of the reportable categories) but must be documented in a timely manner to show the impact of the deviation and corrective/follow-up actions that were taken. Documentation can be in the clinic/progress notes or note/memo to file. Notes/memos should be signed and dated.

Reporting Deviations/Exceptions

All deviations/exceptions will be reviewed and approved by the study Medical Monitor before being sent to the IRB and DSMC. Reports to the IRB and DSMC will be done via the DSMC website www.ctsrmc.org. Reportable deviations must also be sent to the study Medical Monitor.

